## **APPENDIX 1 TIME-TO ONSET AND TIME-TO RESOLUTION DEFINITION AND CONVENTIONS FOR SELECT ADVERSE EVENTS, IMMUNE-MEDIATED ADVERSE EVENTS AND EVENTS OF SPECIAL INTEREST**

### **Time-to onset definition**

Time-to onset of AE (any grade) for a specific category is defined as the time between the day of the first dose of study treatment and the onset date of the earliest AE (of any grade) in this category.

The time-to onset of AE (grade 3-5) for a specific category is defined similarly with an onset date corresponding to a grade 3-5 AE.

Time-to onset of drug-related AE (any grade or grade 3-5) for a specific category is defined similarly but restricted to drug-related AE.

Time-to onset for a specific subcategory is defined similarly but restricted to event of this subcategory.

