CBC with Differential, Chemistry Panel, and Endocrine Testing	X		X C1-C2			Must be performed within 3 calendar days prior to dosing for all time points, except C1D1, which does not need to be repeated if performed within 7 days prior to the first dose. See Section 9.4.4 (Clinical Safety Laboratory Assessments) for list of laboratory tests.
Efficacy Assessments						
Clinical Breast Examination	X					Clinical breast examination by palpation of breast and axilla.

Table 2-2: On-treatment Pre-surgery (Neoadjuvant) Procedural Outline (Safety Run-in Phase and Randomized Phase; CA2097A8)

Procedure ^a	Neoadjuvant Treatment ^{b,c} Cycle 1-5 (1 cycle = 4 weeks)				Pre-surgery (within 7 days prior to surgery)	Notes ^d
	Day 1	Day 8	Day 15	Day 22		
Breast and Axilla Ultrasound (Preferred) or Mammogram	C2D22 (as clinically indicated)				X	Breast and axilla ultrasound (preferred) or mammogram to be done on C2D22 and within 7 calendar days prior to surgery. Every attempt should be made to image each participant using an identical imaging modality and acquisition protocol for all imaging time points.
Documentation of Actual Breast Surgery	See Notes.					Record actual type of BC surgery (ie, BCS, mastectomy) on day of or within 7 days after surgery.

Table 2-2: On-treatment Pre-surgery (Neoadjuvant) Procedural Outline (Safety Run-in Phase and Randomized Phase; CA2097A8)

Procedure ^a	Neoadjuvant Treatment ^{b,c} Cycle 1-5 (1 cycle = 4 weeks)				Pre-surgery (within 7 days prior to surgery)	Notes ^d
	Day 1	Day 8	Day 15	Day 22		
Study Drug						
Randomization	X					First dose to be administered within 3 calendar days following randomization (for Randomized Phase ONLY).
IRT Drug Assignment	X					Register the visit in the IRT for study drug allocation.

Table 2-2: On-treatment Pre-surgery (Neoadjuvant) Procedural Outline (Safety Run-in Phase and Randomized Phase; CA2097A8)

Procedure ^a	Neoadjuvant Treatment ^{b,c} Cycle 1-5 (1 cycle = 4 weeks)				Pre-surgery (within 7 days prior to surgery)	Notes ^d
	Day 1	Day 8	Day 15	Day 22		
Administer Nivolumab 480 mg (Safety Run-in Cohorts and Arms A and B)	X					To be administered Q4W IV. First dose to be administered within 3 calendar days following randomization. 
 • Randomized Phase: • Arm A and Arm B • Starting at C2D1 for Arm B

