[figure not shown]
In the Randomized Phase, participants will be randomly assigned by an IRT system to 3 different treatment arms and stratified by the following factors:

2) evaluation of lymph nodes (cytologically positive vs radiologically or cytologically negative); and 3) tumor size (> 3 cm or ≤ 3 cm).

For both the Safety Run-in Phase and Randomized Phase, participants will be treated for a maximum of 5 cycles (1 cycle = 4 weeks). Participants with progressive disease prior to completion of the 5-cycle study treatment must discontinue all study drugs and proceed to the Safety Follow-up Period. Participants who permanently discontinue the study drugs for any reason are considered to have completed the On-treatment Pre-surgery (neoadjuvant) Period, and hence reach end of treatment (EOT). After Cycle 5 or EOT, participants must continue to receive anastrozole (as concomitant medication and not as study treatment) until subsequent SOC breast surgery. Following the completion of neoadjuvant treatment, all participants who remain operative candidates will undergo definitive surgery for BC within 4 weeks of the last neoadjuvant treatment administration. If anastrozole can no longer be administered after EOT, participants will go to breast surgery right away. Pre-surgical lymph node biopsy is not allowed. Information on the type of the surgery will be collected and recorded in the electronic case report form (eCRF). Surgical specimens will be collected for the analyses outlined in the protocol. Depending on treatment assignment, up to 2 safety follow-up visits will be conducted in person. The first safety follow-up visit (FU1) will be completed for all participants within 30 days (± 7 days) from the last study treatment (oral or intravenous [IV], whichever occurs later). The second safety follow-up visit (FU2) will occur approximately within 100 days (± 7 days) from the last dose of nivolumab and will be required for participants in the Safety Run-in Phase and participants randomized to Arms A or B in the Randomized Phase. Further planned treatment of participants in the adjuvant setting (ie, radiotherapy, endocrine treatment, chemotherapy or any other treatment modality) will be at the discretion of the treating physician, following local clinical guidelines, and collected in the appropriate eCRF.

The study design schematic is presented in [Figure 5.1-1](#).

Figure 5.1-1: Study Design Schematic

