7 TREATMENT

Study treatment is defined as any investigational treatment(s), marketed product(s), placebo, or medical device intended to be administered to a study participant according to the study randomization or treatment allocation.

Study treatment includes both Investigational [Medicinal] Product (IP/IMP) and Non-investigational [Medicinal] Product (Non-IP/Non-IMP) and can consist of the following:

- BMS-936558 (nivolumab)
- Abemaciclib
- Palbociclib
- Anastrozole

An IP, also known as an IMP in some regions, is defined a pharmaceutical form of an active substance or placebo being tested or used as a reference in a clinical study, including products already with a marketing authorization but used or assembled (formulated or packaged) differently than the authorized form, or used for an unauthorized indication, or when used to gain further information about the authorized form.

Description and storage information for the 4 drugs used in this open-label study are provided in [Table 7-1](#).

Other medications used as support or escape medication for preventative, diagnostic, or therapeutic reasons, as components of the SOC for a given diagnosis, may be considered as non-IPs.

Premedications or medications used to treat infusion-related reactions should be sourced by the investigative sites if available and permitted by local regulations.

Table 7-1: Study Treatments for Study Number CA2097A8

Product Description/ Class and Dosage Form	Potency	IP/Non-IMP	Blinded or Open Label	Packaging/ Appearance	Storage Conditions (per label)
Nivolumab Injection ^a	10 mg/mL; 100-mg fill volume and 10 mg/mL; 40-mg fill volume	IP	Open Label	Vials	Refer to the label or container and/or Pharmacy Manual
Abemaciclib Tablets ^b	150 mg, 100 mg, and 50 mg	IP	Open Label	Tablets	Refer to the label or container and/or Pharmacy Manual
Palbociclib Capsules ^b	125 mg, 100 mg, and 75 mg	IP	Open Label	Capsules	Refer to the label or container and/or Pharmacy Manual
Anastrozole Tablets ^b	1 mg	IP	Open Label	Tablets	Refer to the label or container and/or Pharmacy Manual

Abbreviations: IP = investigational product; IMP, investigational medicinal product; mg = milligram; mL = milliliter; SmPC = summary of product characteristics.

^a May be labeled as either “BMS-936558-01” or “Nivolumab”.

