7.1.1 Nivolumab Dosing (Safety Run-in Cohorts and Randomized Phase Arms A and B)

Participants are to start nivolumab within 3 calendar days of randomization. Participants will receive nivolumab at a dose of 480 mg as a 30-minute IV infusion for a maximum of 5 cycles (maximum 4 cycles for Arm B).

Doses of nivolumab may be interrupted, omitted, or discontinued, depending on how well the participant tolerates the treatment. There will be no dose escalations or reductions of nivolumab allowed. For Q4W dosing cycles, participants may be dosed within a \pm 3-day window.

If a participant cannot receive nivolumab within a \pm 3-day window, nivolumab must be omitted (skipped) for that cycle. If nivolumab is omitted, the other study medications may continue. If a participant discontinues nivolumab, the entire study treatment (CDK4/6 inhibitor and anastrozole) must be discontinued.

When nivolumab is scheduled to be administered on the same day with palbociclib plus anastrozole, nivolumab dosing should be started > 1 hour after palbociclib plus anastrozole ingestion. If nivolumab can not be given within 3 days of palbociclib plus anastrozole administration for a given cycle, nivolumab must be omitted for that cycle.

Premedications are not recommended for the first dose of nivolumab.

Participants should be carefully monitored for infusion reactions during nivolumab administration. If an acute infusion reaction is noted, participants should be managed according to [Section 7.4.4.3](#) (Treatment of Nivolumab Infusion Reaction).

Instructions for dilution and infusion of nivolumab injection may be provided in the clinical protocol, pharmacy binder, or pharmacy reference sheet. Care must be taken to assure sterility of

the prepared solution, as the product does not contain any antimicrobial preservative or bacteriostatic agent.

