## 1 BACKGROUND AND RATIONALE

CA2097A8 is an open-label, randomized, non-comparative Phase 2 study assessing nivolumab, plus abemaciclib (per original protocol) or palbociclib, and anastrozole as either concurrent or phased neoadjuvant treatment for men and postmenopausal women with primary breast cancer (BC)  $\geq 2$  cm that are estrogen receptor-positive (ER+) and human epidermal growth factor receptor 2-negative (HER2-) with safety run-in. As of Revised Protocol 03, abemaciclib related cohorts will no longer be investigated in this trial.

Nivolumab (BMS-936558) is a fully human, IgG4 (kappa) isotype monoclonal antibody (mAb), an immuno-oncologic (IO) checkpoint inhibitor that binds programmed cell death-1 (PD-1) on activated immune cells and disrupts engagement of the receptor with its ligands programmed death-ligand 1 (PD-L1; B7-H1/CD274) and programmed death-ligand 2 (PD-L2; B7-DC/CD273), thereby abrogating inhibitory signals and augmenting the host anti-tumor response. Abemaciclib and palbociclib are orally bioavailable and highly selective small-molecule inhibitors against cyclin-dependent kinases (CDK)4/cyclin-D1 and CDK6/cyclin-D3 enzyme complexes, lead to reactivation of retinoblastoma (Rb) protein, binding back of E2F transcription factor and subsequent cell cycle arrest, thus abrogating endocrine-resistant cell proliferation. Anastrozole is a reversible, third-generation, selective nonsteroidal aromatase inhibitor (NSAI) that reduces peripheral estrogen synthesis by blocking the conversion of androgens to estrogens in non-ovarian tissues. A detailed description of the chemistry, pharmacology, efficacy, and safety of the study treatments is provided in the Investigator Brochures (IBs) and package inserts.

The study will assess the efficacy and safety of: i) concurrent therapy with nivolumab in combination with palbociclib, and anastrozole (Arm A), ii) phased therapy with one initial priming cycle of palbociclib and anastrozole followed by nivolumab in combination with palbociclib, and anastrozole (Arm B), and iii) control treatment with palbociclib and anastrozole (Arm C). Participants with newly diagnosed, previously untreated primary ER+ and HER2- BC  $\geq 2$  cm will be subjected to a total 5 cycles (4 weeks per cycle) of neoadjuvant therapy before definitive surgery. Efficacy will be measured by significantly improved residual cancer burden (RCB) 0-I rate. [REDACTED]

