#### **7.6.7.2 Time-to Onset of Select AE**

Time-to onset of drug-related select AEs (any grade, grade 3-5) will be summarized for each category/subcategory by treatment group.

Time-to onset analyses are restricted to treated subjects who experienced at least one drug-related select AE in the category/subcategory. The analyses will be conducted using the 30-day safety window.

Additional details regarding the time-to onset definition are described in time-to onset definition subsection of [APPENDIX 1](#).

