### **7.6.8 Immune-Mediated Adverse Events (US Submission)**

IMAEs will be summarized by treatment group for each immune-mediated category / PT using the 100-day safety window:

- Overall summary of non-endocrine IMAEs by worst CTC grade (any grade, grade 3-4, grade 5) where immune modulating medication was initiated presented by Category / PT.
- Overall summary of endocrine IMAEs by worst CTC grade (any grade, grade 3-4, grade 5) presented by Category / PT.
- Overall summary of non-endocrine IMAEs leading to discontinuation by worst CTC grade (any grade, grade 3-4, grade 5) where immune modulating medication was initiated presented by Category / PT.
- Overall summary of endocrine IMAEs leading to discontinuation by worst CTC grade (any grade, grade 3-4, grade 5) presented by Category / PT.
- Overall summary of non-endocrine IMAEs leading to dose delay or reduction by worst CTC grade (any grade, grade 3-4, grade 5) where immune modulating medication was initiated presented by Category / PT
- Overall summary of endocrine IMAEs leading to dose delay or reduction by worst CTC grade (any grade, grade 3-4, grade 5) presented by Category / PT.
- Summaries of time-to onset and time-to resolution of non-endocrine IMAEs where immune modulating medication was initiated presented by Category.
- Summaries of time-to onset and time-to resolution of endocrine IMAEs presented by Category.

A by-subject listing of IMAEs will be provided. By-subject listings of time-to resolution for longest IMAEs cluster (any grade and grade 3-5 in separate summaries) will also be provided. For new studies which collect investigator assessment of potential IMAE data, a by-subject listing of AEs considered as immune-mediated events per investigator but not qualified for IMAEs definition will also be provided.

In addition, for all nivolumab treated subjects who experienced at least one IMAE, the following data presentation will be provided:

- Summary of subjects who were re-challenged with nivolumab by IMAE category, with extended follow-up.
- Summary of subjects who were re-challenged with nivolumab by IMAE category, with extended follow-up.

For these, re-challenge is considered to have occurred when last nivolumab infusion was administered after the onset of an IMAE.

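### Time to onset of select and immune-mediated AEs starts at first study treatment, which in Arm B is a planned 28 days before any nivolumab; an onset measure from first nivolumab should be added

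*SAP*

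**What the plan says.** **Origin.** The time-to-onset definition in SAP Appendix 1, whose title covers select AEs, IMAEs and events of special interest, sets one origin for all arms: "the time between the day of the first dose of study treatment and the onset date of the earliest AE" in the category. No exception is made for Arm B.

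**What starts the clock.** Protocol Section 7 reads "Study treatment includes both Investigational [Medicinal] Product (IP/IMP) and Non-investigational [Medicinal] Product (Non-IP/Non-IMP) and can consist of the following", and its list names nivolumab, abemaciclib, palbociclib and anastrozole. A dose of any component therefore counts as first study treatment.

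**Arm B schedule.** SAP Section 1 describes "phased therapy with one initial priming cycle of palbociclib and anastrozole followed by nivolumab in combination with palbociclib, and anastrozole (Arm B"). The nivolumab row of Protocol Table 2-2 has "Starting at C2D1 for Arm B". Protocol Section 5.1 states that "participants will be treated for a maximum of 5 cycles (1 cycle = 4 weeks"), and Section 7.1.1 gives nivolumab "for a maximum of 5 cycles (maximum 4 cycles for Arm B"). Arm A starts nivolumab in Cycle 1.

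**Outputs.** SAP 7.6.7.2: "Time-to onset of drug-related select AEs (any grade, grade 3-5) will be summarized for each category/subcategory by treatment group". That summary is limited to participants with at least one such event and uses the 30-day window. SAP 7.6.8 reports IMAEs by treatment group with the 100-day window and lists "Summaries of time-to onset and time-to resolution of endocrine IMAEs presented by Category", with a parallel line for non-endocrine IMAEs.

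**Attribution.** SAP 7.1.1 defines drug-related by relationship to study drug, without separating the components.

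**The concern.** In Arm A the onset clock and nivolumab exposure start together. In Arm B the clock runs for a whole cycle first. Two participants with the same delay between first nivolumab and an immune event will show onset times about one cycle apart, for no reason except the choice of origin. Someone who sets the Arm A and Arm B onset tables side by side, or pools the two arms, could mistake this for a difference in latency.

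The same gap lets two other things through:

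- **Events before nivolumab are not marked in the summaries.** SAP 6.1 counts AEs as on-treatment from first study treatment, so Arm B Cycle 1 events can be the earliest event in a category. Protocol 3.3.2 lists diarrhea and rash as common palbociclib reactions, and both also appear among the IMAE categories in SAP 7.1.1.3.
- **Re-challenge.** SAP 7.6.8 counts a re-challenge whenever the last nivolumab infusion follows the onset of an IMAE. An Arm B participant with an IMAE in Cycle 1 who then receives a first nivolumab dose meets that rule without any earlier nivolumab exposure.

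**Working it through.** The plan states no onset figure, so there is nothing to reproduce. The check is date arithmetic, followed by a sensitivity calculation on medians.

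**1. Planned lag in Arm B**

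One cycle is 4 weeks, or 28 days (Protocol 5.1), and nivolumab starts at Cycle 2 Day 1 (Table 2-2).

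- Lag from first study dose to first nivolumab = 1 × 28 = 28 days.
- With the ±3-day dosing window (Protocol 7.1.1, SAP 7.4.2): 28 − 3 = 25 to 28 + 3 = 31 days. It is longer if the first nivolumab dose is omitted.
- Planned lag in Arm A: 0 days.

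**2. Offset per event**

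SAP Section 8 computes a duration as last date minus first date plus 1. For an event L days after first nivolumab:

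- Arm A: L + 1
- Arm B, as defined: L + 28 + 1
- Arm B, from first nivolumab: L + 1

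| L (days) | Arm A | Arm B as defined | Arm B from first nivolumab |
|---|---|---|---|
| 7 | 8 | 36 | 8 |
| 28 | 29 | 57 | 29 |
| 42 | 43 | 71 | 43 |
| 84 | 85 | 113 | 85 |

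The offset is 28 days at every latency, and the +1 cancels.

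**3. What happens to the median**

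The latency distribution is not in the documents, so this step rests on assumptions: exponential latency with mean m from 30 to 240 days, 5 × 28 = 140 days of treatment, and observation to T = 140 + 30 = 170 or 140 + 100 = 240 days. Arm B has T − 28 days from first nivolumab. The median among those with an event is −m × ln[1 − 0.5 × (1 − e^(−T/m))].

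Example with m = 120 and the 30-day window:

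- Arm A (T = 170): 57.1 days.
- Arm B (T = 142): 51.1 days from nivolumab, so 51.1 + 28 = 79.1 as defined.
- Difference: 22.0 days.

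Across m, with only nivolumab-caused events:

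| Window | Arm B − Arm A, as defined | Arm B − Arm A, from first nivolumab |
|---|---|---|
| 30-day | 18.4 to 27.8 | −9.6 to −0.2 |
| 100-day | 20.1 to 28.0 | −7.9 to 0.0 |

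The median moves by less than 28 days because Arm B is followed for 28 fewer days after first nivolumab.

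**4. Adding background events**

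Some drug-related events will come from palbociclib or anastrozole, and in Arm B these can occur in Cycle 1. With an assumed total hazard of 0.004 per day and the 30-day window, simulation gives:

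| Background share of hazard | Arm A median | Arm B median | Difference |
|---|---|---|---|
| 0% | 70.8 | 89.0 | 18.2 |
| 25% | 70.8 | 84.6 | 13.8 |
| 50% | 70.9 | 80.2 | 9.3 |

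Background events mask the offset. They do not correct it.

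**The case against.** **First study treatment is a legitimate origin.** Arm B is a five-cycle regimen that includes the priming cycle. Time from its first dose tells a reader when an event occurs after starting that regimen, and it works the same way in all three arms. If nivolumab starts a cycle later, patients do meet its toxicity later. This stands, and it is why the current definition should be kept and not replaced.

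**A reader might infer that the onset tables exist to contrast concurrent with phased nivolumab.** The documents do not say so. SAP 7.6.7.2 and 7.6.8 ask only for summaries by group and category, and Protocol 7.3 describes the study as non-comparative. Equal latency in the two arms is also an assumption, since the priming cycle is meant to alter the immune response (Protocol 5.5.4).

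**A reader might also infer that the Arm B tables will sit a fixed 28 days later.** They need not. That figure is the planned offset for one nivolumab-caused event. The summarized events are a mixture, and the calculations above give smaller shifts in the median.

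**Nor do Cycle 1 events pass freely into the IMAE tables.** SAP 7.1.1.3 requires the investigator to consider the event potentially immune-mediated, with no clear alternate etiology or with an immune-mediated component. In an open-label trial the investigator knows that no nivolumab has been given. Protocol 7.4 also requires causality for each drug, and the planned AE and dosing listings would let a careful reader find such events. The lack of marking therefore matters mainly for the select-AE summaries.

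**The cited IO Core SAP was not available.** SAP 4.2.4 refers to it for safety details. Nothing in the visible text overrides Appendix 1, but a rule held elsewhere cannot be excluded.

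None of this supplies an onset measure from first nivolumab, or stops a Cycle 1 IMAE in Arm B from meeting the re-challenge rule.

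**Conclusion.** The point holds as a minor gap in the descriptive safety outputs. As defined, a nivolumab-caused select AE or IMAE with the same latency is recorded a planned 28 days later in Arm B than in Arm A (25 to 31 with the dosing window). Under the stated assumptions the difference in medians is about 18 to 28 days if all events are nivolumab-caused. It is about 14 to 9 days in the illustration where 25 to 50% of the hazard is background.

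The documents do not support reading this as a bias in a planned Arm A versus Arm B comparison, or as a guaranteed 28-day shift in any table. No test, sample size, primary result or incidence rate changes. The reach is the select-AE and IMAE onset summaries and the re-challenge summary. SAP 7.6.9 plans no onset table for other events of special interest.

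The 28 days rests on the Cycle 2 Day 1 start. Protocol 7.1.1 and SAP 7.4.2 also say that nivolumab starts within 3 calendar days of randomization, without excepting Arm B. Those passages and Table 2-2 need to be reconciled.

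**What to change.** Keep time from first study treatment in all arms as the regimen-level measure. Before database lock, add the following to the SAP:

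1. For the onset summaries in 7.6.7.2 and 7.6.8, in the groups given nivolumab (run-in, Arm A and Arm B), add time from first nivolumab dose to the earliest event in the category with onset on or after that dose. This settles the case of a participant with one event before nivolumab and another after it. Participants who never receive nivolumab stay in the existing summary only.
2. Flag Arm B events with onset before first nivolumab and show them separately.
3. Do not count the flagged events as re-challenge under 7.6.8.
4. Footnote the new summary to say that Arm B has one planned cycle less of follow-up from first nivolumab, so medians may still differ by a few days at equal latency (up to 9.6 days in the cases worked above).

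No onset table for other events of special interest is needed.

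The cost is one derived date, one flag and one extra summary. Dosing dates are already on the CRF (SAP 7.4.1). Specifying this before the onset times are seen avoids a post-hoc choice of origin.
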